#### 3.2.2 Secondary Endpoints

- Occurrence of Grade 3 placebo microneedle patch-related unsolicited adverse events from Day 1 through the Final Study Visit (Day 27 – 38).

- Occurrence of new-onset medical conditions (NOMC) from Day 1 through the Final Study Visit (Day 27 – 38).
- Occurrence of solicited and unsolicited adverse events described at the site at which the placebo microneedle patch was applied.
- Quantitative and qualitative description of LAR responses to survey questions.

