## 2 BACKGROUND INFORMATION AND SCIENTIFIC RATIONALE

### 2.1 Background Information

Available vaccine delivery methods include intramuscular or subcutaneous injection using hypodermic needle which is limited by patient needle phobia (Hamilton 1995) and the need for trained medical personnel. Alternative routes of vaccination that avoid hypodermic needles have previously been poorly immunogenic, require live vaccines, utilize bulky devices and/or are unsuitable for self-administration (Mitragotri 2005, Kersten 2007). Novel vaccine delivery methods such as microneedles can render vaccination easier and more acceptable to the public by simplifying vaccine access, and can confer equal or superior immunological responses to that induced by hypodermic needle through conventional intramuscular administration (Kim 2012).

Microneedles are micron-scale needles that administer vaccine directly into the skin using a simple minimally invasive approach without generating sharps waste. The microneedles are solid conical structures made of water-soluble excipients that can encapsulate a vaccine. Excipients used will be on the Food and Drug Administration's (FDA) Generally Recognized as Safe (GRAS) list and/or on FDA's list of inactive ingredients in approved products. The microneedles that are used in the study are painlessly inserted into the skin as a patch with a hypoallergenic adhesive bandage backing. The microneedles are left in place for up to 20 minutes. During this time, the microneedles dissolve in the skin, so that upon removal of the patch, the microneedles have disappeared and the sharps-free patch backing can be discarded as non-sharps medical waste. Therefore, microneedle patch application can be carried out as simply as applying a Band-Aid® adhesive bandage.

Microneedles have been studied for vaccines including influenza, rabies, *Bacillus Calmette- Guerin (BCG)*, West Nile virus, and Human Papilloma Virus (HPV) (Kim 2012). There are a number of approved medical and cosmetic products using microneedles currently sold around the world. Soluvia® is a single hollow microneedle that is 1.5 mm long and is attached to a syringe (<http://www.bd.com/pharmaceuticals/products/microinjection.asp>). It is marketed worldwide prefilled with influenza vaccine for intradermal vaccination as IDflu®, Intanza® and Fluzone Intradermal®

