#### 3.1.2 Secondary Objectives

- To evaluate unsolicited adverse events following application of a placebo microneedle patch topically.
- To evaluate new-onset medical conditions (NOMC) following application of a placebo microneedle patch topically.
- To evaluate the suitability of application of a placebo microneedle patch to different body locations.
- To evaluate the acceptability to the Legally Authorized Representative (LAR) of applying a placebo microneedle patch topically.

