## 7 STUDY SCHEDULE

Procedures to be performed at each study visit are detailed below. Refer also to Appendix A: Study Schedule.

### 7.1 Visit 1: Enrollment/Application of Placebo Microneedle Patch, Day 1

The following assessments will be performed on the day of enrollment prior to administration of the placebo microneedle patch.

- Informed Consent obtained.
- The optional consent for the optional placebo microneedle patches 2/3 may be signed.
- Inclusion/Exclusion criteria review.
- Complete medical history via interview with LAR including vaccination history.
- Record medications administered within the past 30 days and any concomitant medications.
- Vital signs: temperature and pulse.
- Complete physical examination.
- Height and weight.
- Baseline acceptability questionnaire.

The following procedures will be performed after subject eligibility has been verified:

- Subject enrolled.
- A baseline photograph of the area of application may be obtained.
- Application of placebo microneedle patch to the skin by a trained study nurse. The microneedle patch will remain in place for up to 20 minutes. The patch will then be removed and the used patch will be saved.
- The memory aid, thermometer and ruler will be provided to the LAR and instructions will be provided.
- The site of the placebo microneedle patch removal will be assessed at least 15 minutes and 30 minutes post-placebo microneedle patch removal. Per investigator discretion, photographic documentation (refer to MOP) and dermatologic referrals may be obtained.
- Study personnel will assess and record all AE/SAEs that occur after enrollment.
- The acceptability questionnaire will be completed by the LAR.

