#### Optional Microneedle Patch 2/3 Study Events Day 8 (+2 days)

- The optional consent for the optional placebo microneedle patches 2/3 will be signed before additional study procedures occur on Day 8 (if not already signed).
- Inclusion/Exclusion criteria review.
- A baseline photograph of the area of application may be obtained.

- Application of placebo microneedle patches 2/3 to the skin in a different location than previously by a trained study nurse. The placebo microneedle patches will remain in place for up to 20 minutes. The patches will then be removed and the used patch will be saved.
- The memory aid, thermometer and ruler will be provided to the LAR and instructions will be provided.
- The site of the placebo microneedle patches removal will be assessed at least 15 minutes and 30 minutes post-placebo microneedle patch removal. Per investigator discretion, photographic documentation (refer to MOP) and dermatologic referrals may be obtained.
- Study personnel will assess and record all AE/SAEs that occur after enrollment.
- The acceptability questionnaire will be completed by the LAR.

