### 11.3 Analysis Plan

The safety population includes all subjects who receive the placebo microneedle patch. The safety population will be the primary analysis population for safety analyses. AEs will be analyzed using the safety population. Subjects will be analyzed as treated.

Primary Outcome Endpoints

AEs, reactogenicity events and SAEs will be recorded throughout the study. AEs will be coded using the Medical Dictionary for Regulatory Activities (MedDRA) dictionary. AE summary tables will be based on treatment-emergent AEs for the safety population. Descriptive statistics (e.g., number and percentage of subjects) will be used for each treatment group. AEs will be summarized by severity, relationship to treatment, and AEs leading to discontinuation. SAEs will also be tabulated by overall and treatment related events.

Secondary Outcome Endpoints

Unsolicited AEs and new-onset medical conditions (NOMC) will be recorded. AEs will be coded using the Medical Dictionary for Regulatory Activities (MedDRA) dictionary. AE summary tables will be based on treatment-emergent AEs for the safety population. Descriptive statistics (e.g., number and percentage of subjects) will be used for each treatment group. AEs will be summarized by severity, relationship to treatment, and AEs leading to discontinuation. NOMC will also be tabulated by overall and treatment related events.

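### Suitability of body locations is judged by site adverse events alone, so a low event count at a site cannot be told apart from patches that came off early or did not insert

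*Combined protocol and SAP*

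**What the plan says.** Section 3.1.2 sets the objective: "To evaluate the suitability of application of a placebo microneedle patch to different body locations". Section 4 allows seven body sites, from the shoulder blade to the foot. The endpoint that corresponds to this objective, in 3.2.2 and again in 11.1, is "Occurrence of solicited and unsolicited adverse events described at the site at which the placebo microneedle patch was applied".

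On exposure, section 7.1 says of Day 1: "The microneedle patch will remain in place for up to 20 minutes. The patch will then be removed and the used patch will be saved". For the optional Day 8 patches, section 7.3 says: "The placebo microneedle patches will remain in place for up to 20 minutes". Those patches are also kept after removal.

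Section 2.1 describes how the patch works: "During this time, the microneedles dissolve in the skin, so that upon removal of the patch, the microneedles have disappeared".

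Section 11.3 defines the analysis set: "The safety population includes all subjects who receive the placebo microneedle patch". It plans counts and percentages of subjects by treatment group and mentions no table by body site.

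**The concern.** Whether a location suits this patch in a moving infant has at least two parts: whether the skin tolerates it, and whether the patch stays on and the needles enter. Adverse events address only the first. They are also not neutral on the second, because a patch that falls off early or never inserts gives the skin less to react to. Poor application at a site would tend to lower its event count and so favour that site on the only measure tied to location.

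Section 2.3.2 says the results will inform the design of a later infant poliovirus vaccine patch trial. There, delivery at the chosen site is essential, and a site that looks quiet because patches did not work would be a poor guide. Wear time and detachment can be seen only while the patch is on the child. If they are not noted then, they cannot be recovered reliably.

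**Working it through.** The plan gives no figure on this point. The probabilities in 11.2 concern event counts per cohort and do not bear on it. The check is a comparison of the text, followed by an illustration on assumed rates.

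**1. What the protocol specifies about application**

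- Wear time: an upper limit only, on Day 1 and Day 8. A patch that comes off after one minute is within the wording.
- Time on, time off, adhesion, detachment: no step in 7.1, 7.3 or the Appendix A schedule.
- Insertion or dissolution: no step. The checks 15 and 30 minutes after removal are of the application site.
- Used patch: "The patch will then be removed and the used patch will be saved", with no examination, measure or endpoint attached.
- Survey (8.1.6): covers ease of use and pain, but serves acceptability and is not stated to be analysed by body site.
- Analysis (11.3): subjects by treatment group. A child may have up to three patches at different sites, so a by-site result needs applications as its denominator. None is defined.

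**2. Why the data cannot separate the two explanations**

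Let r be the reaction probability for an inserted patch, b that for a failed one, and f the fraction failing at a site. With independent applications, the count at a site with m applications is binomial with probability

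q = (1 − f) × r + f × b.

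Only q can be estimated from event counts. Take r = 30% and b = 5% (both assumed) and f = 50%:

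q = 0.5 × 0.30 + 0.5 × 0.05 = 17.5%.

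A site where every patch inserts and the true reaction rate is 17.5% produces exactly the same distribution of counts. Without f, or something close to it, the two sites cannot be distinguished.

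**3. Direction, illustrated**

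Assume seven sites with equal numbers of patches and one site with failures. The number per site comes from Table 1 and the maximum of three patches per child: 25/7 ≈ 4 (one cohort, one patch each), 75/7 ≈ 11 (one cohort, three each), 150/7 ≈ 21 (two cohorts, three each). The chance that the failing site has the lowest or tied-lowest count is

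Σ over x of P(X_q = x) × P(X_r ≥ x)^6,

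where X_q and X_r are binomial with m trials. For the sole lowest count, replace X_r ≥ x by X_r ≥ x + 1.

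| Patches per site; r; b (assumed) | Result | No failures | Half fail | All fail |
|---|---|---|---|---|
| 11; 30%; 5% | lowest or tied | 23% | 54% | 91% |
| | sole lowest | 9% | 28% | 67% |
| 4; 10%; 5% | lowest or tied | 66% | 73% | 82% |
| | sole lowest | 0.1% | 0.1% | 0.1% |
| 21; 60%; 0% | lowest or tied | 19% | 93% | 100% |
| | sole lowest | 11% | 87% | 100% |

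Over all settings tried (r of 10%, 30% or 60%; b of 0% or 5%), the chance of lowest or tied-lowest is 19% to 66% with no failures, 38% to 93% with half failing and 54% to 100% with all failing. Failure moves a site towards looking better tolerated. How far it moves depends entirely on rates the documents do not give.

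**The case against.** Several points on the other side stand.

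- Section 10.2 leaves form content to the Manual of Procedures, which is not among the documents. Keeping the used patches suggests that some later use may be intended. So one can say only that the protocol does not specify these measures, not that they go unrecorded. A field in the manual would still leave the objective without a matching endpoint or by-site analysis.
- A reader might infer that a failing site will come out as the best tolerated. The documents do not support this. Counts per site are small and ties are common. Section 2.3.1 notes that the adhesive alone can, rarely, cause a local reaction, and partial wear need not mean no insertion. Appendix B grades erythema and induration under 2.5 cm as 0, so graded counts may be low at every site. The plan also states no ranking or site-selection rule.
- A reader might infer that the primary reactogenicity result is biased. It is not, for the question it asks. The primary objective concerns what follows application, and including everyone who received a patch answers that. Section 11.3 counts subjects and does not treat each application as a full exposure.
- Nothing in the documents suggests that detachment is frequent.

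None of this removes the gap between the location objective and its endpoint. The survey fills it only in part.

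**Conclusion.** The point holds as a mismatch between objective and endpoint. Suitability of application by location is to be assessed from site adverse events alone, with no specified measure of wear time, detachment or insertion, no stated use of the saved patches and no by-site table. A low event count at a site is therefore ambiguous between good tolerability and failed application.

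The direction rests on one assumption, which follows from section 2.1: a patch that comes off early or does not insert causes fewer reactions on average than one that dissolves as described. No size of bias can be taken from the documents, and the percentages above are illustrations only. The primary safety analysis is unaffected. This is a cheap improvement that the trial should make in order to answer its own secondary objective.

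**What to change.** **Recording.** In 7.1 and in the patch 2/3 events of 7.3, have the study nurse who applies and removes the patch enter, for each application:

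- body site;
- time on and time off;
- outcome: removed by staff as intended, partly lifted, or came off or was removed early, with the reason;
- optionally, on simple inspection, whether needles visibly remain on the saved patch.

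Define removal as intended on the form as staff ending the wear by their own decision, not because of lifting, distress or a reaction. This is needed because the protocol gives only an upper limit. The wear duration itself stays unchanged.

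**Endpoint and analysis.** Add to 3.2.2, 11.1 and 11.3, by body site and per application:

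- the proportion still adhered until staff removal as intended;
- wear time (median and range);
- site reactions for all applications, shown beside these figures.

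Any table limited to patches worn until intended removal should be labelled descriptive. Early removal may itself follow a reaction or distress, so that subset can leave out the children who reacted.

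**Cost.** A few CRF fields, one extra table and, if adopted, a brief look at patches already being kept. No new visit is needed. Per-site denominators will be small, so the figures should be read as descriptive.

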## 4 STUDY DESIGN

This is a single-center, unblinded, study in which healthy infants and children (6 weeks – 24 months inclusive) will have placebo microneedle patches applied to the skin. This study is designed to investigate the safety, reactogenicity, and acceptability of a placebo microneedle patch.

Infants and children will be recruited from metropolitan Atlanta and will be enrolled at Emory Children's Center. Approximately 25 to 50 infants and young children will be enrolled into one of two possible cohorts that will have placebo microneedle patches administered topically for up to approximately 20 minutes. Cohort 1 will assess one formulation of the microneedle patch (Microneedle Formulation 1). If the Microneedle Formulation 1 is well tolerated in Cohort 1, Cohort 2 may be enrolled using a different formulation of the microneedle patches if available (Microneedle Formulation 2).

After informed consent is obtained, subjects will be screened by history and physical examination at screening. Collected data will include demographic information, medical history, list of current and recent medications, and vaccination history. The placebo microneedle patch will be administered on Day 1 to subjects meeting enrollment criteria. Each subject will have 3 clinic visits: Day 1, Day 2 (+1 day), and Day 8 (+2 days). One telephone call will occur (Day 29 +/- 3 days). In those that receive additional microneedle patches on Day 8 (+2 days), follow-up visits will also occur at Day 9 (+2 days) and Day 15 (+3 days). Refer to the Appendix A for a detailed listing of study days and procedures.

Safety will be measured by the occurrence of solicited application site and systemic reactogenicity on the day of microneedle patch administration through Day 8 (+2 days) for the first patch and through Day 15 (+3 days) for the second and third patch. Unsolicited AE, and serious adverse events (SAEs) and new-onset medical conditions (NOMC) will be collected through Day 29 and Day 38 after microneedle patch administration. The acceptability of applying a microneedle patch topically will be assessed by LAR survey completed before microneedle patch application on Day 1, after microneedle patch removal on Day 1, at Day 2 (+1 day), Day 8 (+2 days), and the Final Study Visit (Day 27 – 38) in everyone. In those that receive additional microneedle patches, it will be also be repeated at Day 9 (+2 days) and Day 15 (+3 days).

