## 7.6 Final Visit: Day 27 - 38, Telephone Call

The following assessments will be performed.

- Obtain interim medical history and note any changes since the last visit.
- Record concomitant medications.
- Study personnel will review the memory aid information with the LAR (if ongoing symptoms were noted at Day 8 for placebo microneedle patch 1 and Day 15 for placebo microneedle patch 2/3) and record all AE/SAEs.
- The final acceptability questionnaire will be completed by the LAR.

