#### **8.1.6 Acceptability Assessments:**

To gauge LAR acceptability of vaccination using a microneedle patch, the LAR will complete a survey at Days 1, 2 (+1 day), 8 (+2 days), and Day 27 - 38 (Day 9 (+2 days) and Day 15 (+3 days) in those having placebo microneedle patches 2/3) including items that assess vaccination acceptability items (outcomes) via continuous scales (0-10 likelihood) and vaccination knowledge, attitudes, perceptions, and beliefs using Likert-type measurement (1-5 agreement levels) for multiple time point ANOVA and correlational analyses. The LAR will report on absolute and relative scores of ease of use, pain, product apprehension, comparative product utility, and overall preference comparing placebo microneedle patch application to previous experience with needle and syringe injection (Day 1); preference comparing the post-patch period to prior experience with vaccination (Day 8 (+2 days), and 27 – 38; also Day 9 (+2 days) and Day 15 (+3 days) in those having placebo microneedle patches 2/3); and perception of ease with which they might administer a microneedle patch in the future. The same LAR will complete the survey at all follow-up time points whenever possible. Basic sociodemographic characteristics will also be included, such as race/ethnicity, healthcare utilization/access, parental educational attainment, healthcare experience including previous immunization history, and socioeconomic indicators (household income, education).

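### The acceptability survey has a pre-patch baseline in everyone, but no change from it is specified, and the one named method, a multi-time-point ANOVA, gives no size or direction of change

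*Combined protocol and SAP*

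**What the plan says.** The acceptability objective in Section 3.1.2 is "To evaluate the acceptability to the Legally Authorized Representative (LAR) of applying a placebo microneedle patch topically". Its endpoint, in Section 3.2.2 and again in Section 11.1, is a "Quantitative and qualitative description of LAR responses to survey questions". No item, time point or contrast is named.

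Section 4 plans a "LAR survey completed before microneedle patch application on Day 1, after microneedle patch removal on Day 1", then at Day 2, Day 8 and the final visit in everyone, with Days 9 and 15 added for children who receive more patches. Section 7.1 lists a "Baseline acceptability questionnaire" among the assessments done before the first patch. Section 8.1.6 adds: "The same LAR will complete the survey at all follow-up time points whenever possible".

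On analysis, Section 8.1.6 says that the 0–10 and 1–5 items are collected "for multiple time point ANOVA and correlational analyses". The secondary part of Section 11.3 covers unsolicited adverse events and new-onset medical conditions only; it does not mention the survey.

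Sections 7.3 and 9.4 restrict patches 2/3, and so the Day 9 and Day 15 visits, to children with no ongoing adverse event at Day 8 whose LAR chooses to continue.

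**The concern.** LARs who volunteer a child for this study may already be well disposed to the patch. A high score afterwards, reported alone, cannot be separated from the attitude with which they arrived. The trial collects each LAR's own starting score, but nothing in the plan commits it to using that score as the reference.

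Two things are at stake. First, with many items, several time points and no named contrast, the acceptability result can be chosen after the data are seen. Second, the choice of time points for the ANOVA is open, and including all of them on complete cases would select on something close to the outcome: the LARs left would be those whose child tolerated the first patch and who wanted more. Section 2.3.2 says that the results will inform a later infant vaccine-patch trial, so an acceptability result that is too favourable could carry forward.

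**Working it through.** The plan has no figure of its own to reproduce on this point. Section 11.2 gives only chances of observing adverse events. No SD, within-LAR correlation or uptake of patches 2/3 is given anywhere.

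**Step 1: who is surveyed when** (Sections 4 and 7.1 to 7.6)

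| Occasion | Surveyed |
|---|---|
| Day 1, before patch | all |
| Day 1, after removal | all |
| Day 2 | all |
| Day 8, before any patch 2/3 | all |
| Day 8, after patches 2/3 | patch 2/3 recipients only |
| Day 9 | patch 2/3 recipients only |
| Day 15 | patch 2/3 recipients only |
| Day 27–38 | all |

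Five occasions are common to all LARs; recipients of patches 2/3 have 5 + 3 = 8. Day 8 holds two surveys for those recipients, so "Day 8" alone does not identify a score. The Protocol Summary differs: it places a survey before each application and does not list one at the final call.

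**Step 2: what the named analyses deliver**

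A description can give the level at each time point, but does not have to give a change. An ANOVA over k time points tests whether all k means are equal. Its F statistic has no sign and is not in points on the scale. A change from the pre-patch score needs a stated contrast with an interval, and none is stated. The plan also does not say whether the repeated answers of one LAR are modelled as repeated, or how missing answers are handled.

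**Step 3: complete cases over all time points**

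A LAR whose child has no patch 2/3 has no Day 9 or Day 15 score, by design. A complete-case analysis over all occasions therefore drops every such LAR. Those kept satisfy two conditions: no ongoing adverse event at Day 8, and a decision to continue. The number lost depends on uptake, which is unknown. If, for illustration, 20 of 25 remained, the half-width factor t(0.975, n−1)/√n would go from 2.064/√25 = 0.413 to 2.093/√20 = 0.468, or 0.468/0.413 = 1.13 times as wide. The selection matters more than this loss of precision.

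**Step 4: precision of a paired change**

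Assumptions: one LAR per child, complete pairs, equal SD before and after.

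SD of change = SD × √(2(1 − r)); half-width = t(0.975, n−1) × SD of change / √n.

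With n = 25 and SD = 2.5:
- r = 0.3: SD of change 2.96, half-width 0.413 × 2.96 = 1.22
- r = 0.5: SD of change 2.50, half-width 0.413 × 2.50 = 1.03
- r = 0.7: SD of change 1.94, half-width 0.413 × 1.94 = 0.80

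Over SD 1.5 to 3 and r 0.3 to 0.7, the half-width runs from 0.48 to 1.47 points with 25 LARs and from 0.33 to 1.01 points with 50.

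For comparison, the mean score at a single time point with n = 25 and SD = 2.5 has half-width 0.413 × 2.5 = 1.03. The change is thus less precise than the level at r = 0.3, equal at r = 0.5 and more precise at r = 0.7. The reason to report change is that it answers the question about starting attitude, not that it is always tighter.

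**The case against.** The strongest reply is that a longitudinal analysis is planned. Section 8.1.6 names one and asks for the same respondent throughout. The documents do not say that it will be run on complete cases or with answers treated as independent, so those are possible faults, not demonstrated ones. This stands: a reader might infer that change over time is ignored altogether, and the documents do not support that. What they lack is the contrast, the estimate and the set of time points.

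It can also be said that the objective concerns how acceptable the patch is, not how opinion shifts, and that the comparison with past needle and syringe experience is already built in. This stands too. If scores start near 10 they cannot rise much, and a change near zero could be misread as poor acceptability. Level and change should therefore be shown together.

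Other tempting readings should be resisted:
- **Causation.** Every child receives a patch. A before-to-after change still contains repeated questioning, regression to the mean and contact with staff, and pairing does not make volunteers representative.
- **A guaranteed gain in precision.** Treating the two surveys as independent samples would give a half-width of 2.011 × 2.5 × √(2/25) = 1.42, against which 1.22 and 0.80 are 14% and 44% narrower. No section plans that unpaired comparison, so this does not measure a loss in this plan.
- **A change of survey mode at the end.** The final visit is a telephone call, but Section 7.6 says only: "The final acceptability questionnaire will be completed by the LAR". How answers are given, there or in clinic, is not stated.

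Finally, the questionnaires are not in the documents. Items such as ease of use may have no pre-patch counterpart, so change can be defined only for items asked both before and after.

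**Conclusion.** The point holds as a gap in the specified analysis that has a concrete better method. The baseline is collected from everyone, the endpoint does not use it, Section 11.3 omits the survey, and the ANOVA in Section 8.1.6 does not by itself report the size or direction of change. The risk of selection is conditional: it arises if the ANOVA is run on complete cases over all time points, which the wording permits but does not state.

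With 25 to 50 LARs, a paired change on a 0–10 item could be estimated to within 0.33 to 1.47 points either side, under the assumed SD of 1.5 to 3 and correlation of 0.3 to 0.7. This is a secondary endpoint of a small uncontrolled study. The safety and reactogenicity endpoints are not affected.

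**What to change.** In Sections 3.2.2, 11.1 and 11.3:
- Name the 0–10 items asked both before and after the patch. For these, report the level at each time point and the within-LAR change from the pre-patch Day 1 score to one named main time point, with a paired 95% CI. Day 8 before any patch 2/3 is a natural choice: everyone is surveyed then and all have had one patch, whereas by Day 27–38 some have had up to three.
- Keep the level of acceptability and the comparison with needle and syringe as reported results. Leave items without a pre-patch counterpart descriptive.
- Call the result a change after application.

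In Section 8.1.6:
- Replace the ANOVA with a linear mixed model with LAR as random effect over the five time points common to all LARs. Use all available responses and flag any change of respondent.
- Describe Days 9 and 15, and the second Day 8 survey, separately in patch 2/3 recipients.
- Reconcile the survey occasions between the Protocol Summary and Section 4.

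The cost is wording and slightly more analysis. No visits, children or questionnaires are added. The mixed model relies on missing answers being explained by the observed ones, which should be stated.
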